### Emergency Unblinding

This is a blinded protocol such that all participants and all study personnel except for the Clinical Research Coordinator and the Research Program Leader are blinded to group allocation. During specific circumstances it will be necessary to unblind other study personnel, such as study team medical personnel. Emergency unblinding will occur under the discretion of the study physician (or one of the study physician assistants) in any situation in which unblinding is deemed necessary to ensure or promote the safety of a study participant. The decision to unblind for safety reasons may occur for a number of reasons and it is not possible to enumerate all potential circumstances. Examples of reasons for unblinding to ensure participant safety include situations in which it is necessary to know which study drugs the subject was taking in order to manage the side effect(s), advise the subject on the risk of future negative drug reactions, uncover potential safety information about the drug, and/or determine whether the adverse event is study related. In those situations, the Clinical Research Coordinator or Research Program Leader will inform the study physician (or physician assistant handling the event) of that subject's study condition. If unblinding occurs, that subject's data will be censored and will not be included in final data analyses.

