### Design Overview

The study will comprise a randomized, double-blind parallel-arm study to ascertain the role of nicotine dose and route of administration in reducing use of combustible cigarettes and in facilitating adoption of e-cigarettes. One hundred thirty daily cigarette smokers will be randomly assigned to receive 8 weeks of exposure to the following conditions (65/group):

- 1. Nicotine containing e-cigarettes + 21 mg nicotine skin patches
- 2. Zero-nicotine e-cigarettes + 21 mg nicotine skin patches

Nicotine and non-nicotine e-cigarettes will be purchased from JUUL Labs. The JUUL is a rectangular closedsystem e-cigarette. This e-cigarette was commercially available as of August 8, 2016 and does not contain any alterations to the chemistry or physical characteristics. Each JUUL Pod pack contains 4 pods. Each JUUL Pod contains 0.7mL with 5% nicotine by weight, approximately equivalent to one pack of cigarettes or 200 puffs. Multiple flavors will be used in this study in order to more accurately mimic real world conditions. Subjects will receive packs containing tobacco-flavored and mint-flavored or menthol-flavored pods. Subjects will be provided with enough additional packs of pods to use during the smoking period. JUUL Pods are sealed system cartridges for use in the JUUL e-cigarette. Each pod is contained in tamper resistant blister packs. The nicotine patches will be purchased from Duke Outpatient Pharmacy.

Ad libitum smoking will be assessed weekly using daily diary recordings of cigarettes smoked per day as well as the objective index of expired air carbon monoxide (CO) levels measured at the study visits.

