### Sessions

The first study visit (V1) will take place approximately one week after the screening visit. Subjects will complete baseline questionnaires and will be randomized to one of the two groups. Subjects will be tested for exhaled air carbon monoxide, and saliva samples will be collected for analysis of smoking related chemicals (e.g., cotinine). Subjects will also complete questionnaires assessing their dependence on cigarettes (Fagerström Test for Nicotine Dependence (FTND) (Heatherton et al., 1991)), and rewarding effects of cigarettes (modified Cigarette Evaluation Questionnaire (Cappelleri et al., 2007)).

Subsequent study visits will occur approximately two weeks apart (with a five-day window on either side of the scheduled visit). If a participant does not attend a visit and it cannot be rescheduled within the allowable window, the visit will be considered a missed visit; if participants miss two consecutive visits they will be withdrawn from the study. Participants will be tested for exhaled air carbon monoxide, and will also complete questionnaires assessing their dependence on cigarettes (Fagerström Test for Nicotine Dependence (FTND) (Heatherton et al., 1991)), and rewarding effects of cigarettes (modified Cigarette Evaluation Questionnaire (Cappelleri et al., 2007)).

Questionnaires will be completed within REDCap on a desktop computer in the Center office. The technician will log on to the REDCap site and will open the questionnaires for the subjects. Subjects will only have access to their questionnaires. Access to any other websites will be blocked by Duke Psychiatry Information Technology.

At the first (V1) and final (V5) sessions, participants will provide saliva and urine samples. The saliva sample will be used for analysis of smoking related chemicals (e.g., cotinine). The urine sample will be used to assess total urinary 4-(methylnitrosamino)-1-(3-pyridyl)-1-butanol (NNAL), a metabolite of the tobacco-specific carcinogen 4-(methylnitrosamino)-1-(3-pyridyl)-1-butanone (NNK). The half-life of NNAL is 10 days (Goniewicz et al., 2009), yielding a valuable index of sustained reductions in cigarette smoking. The half-life of expired air CO, in contrast, is 4.5 h (Sandberg et al., 2011). Total urinary nicotine equivalents (a measure of total nicotine intake) will also be assessed.

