### **Risk/Benefit Assessment**

Include a thorough description of how risks and discomforts will be minimized (per 45 CFR 46.111(a) (1 and 2)). Consider physical, psychological, legal, economic and social risks as applicable. If vulnerable populations are to be included (such as children, pregnant women, prisoners or cognitively impaired adults), what special precautions will be used to minimize risks to these subjects? Also identify what available alternatives the person has if he/she chooses not to participate in the study. Describe the possible benefits to the subject. What is the importance of the knowledge expected to result from the research?

*Conventional (combustible) cigarettes:* Continuing to smoke carries significant health risks. Subjects enrolling in this study are not being asked to quit smoking over the course of the study, but will be exposed to no additional risk from their usual smoking behavior. Their exposure to harmfully and potentially harmful constituents in combustible cigarettes may decrease to the extent they use e-cigarettes as an alternative to combustible cigarettes.

Potential side effects of Nicotine patch: The nicotine patch poses very little risk and is approved for overthe-counter sales as a smoking cessation treatment. It is not being used as a treatment for nicotine dependence in this protocol but the risks will be minimal. Insomnia and abnormal dreams are common and expected side effects associated with 24-hour nicotine patches. If a subject complains of disturbed sleep, he or she will be instructed to remove the patch at bedtime and apply a new one the next day at the usual time. Skin irritation may occur, although this will be minimized by changing the site of patch application daily. If a subject develops itching or a rash at the patch site, he or she will be advised to use 1% hydrocortisone cream on the affected area. Symptoms associated with nicotine toxicity include lightheadedness, dizziness, nausea, fainting and vomiting. A less likely side effect of nicotine patches is somnambulism. If a subject reports significant side effects, the dose of the nicotine patch may be reduced if necessary.

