*Electronic Nicotine Delivery Systems (ENDS):* ENDS, or "e-cigarettes," have been marketed in the U.S. since 2007 and have been used worldwide by millions of smokers. While the potential risks of long-term use of e-cigarettes are unknown, most experts agree that the constituents of e-cigarettes are less harmful than those of combustible cigarettes (Grana et al., 2014). Although it is conceivable that participants could receive an overdose of nicotine, this is extremely unlikely inasmuch as smokers can control the dose according to how they puff and inhale from the devices, as they do with conventional cigarettes. The main side effect that is anticipated with the relatively short 8-week duration of exposure to ENDS in the proposed project is mild irritation of the respiratory tract from inhalation of the propylene glycol and nicotine contained in the product. Should any clinically significant changes occur, the study physician will recommend discontinuation of ENDS use if it is indicated.

The Centers for Disease Control and Prevention (CDC), the U.S. Food and Drug Administration (FDA), state and local health departments are investigating a respiratory syndrome associated with the use of ecigarettes. People with this syndrome have reported a wide variety of symptoms including cough, shortness of breath, chest pain, nausea, vomiting, diarrhea, fatigue, fever, and abdominal pain.

In a New England Journal of Medicine article entitled "Vaping-Induced Lung Injury" (September 6, 2019), [name] stated that "[a]bout 80% of the persons who vaped and became ill reported having used both nicotine products and tetrahydrocannabinol (THC) or cannabidiol (CBD) products". Thus far, investigators have not found a single product linked to all reports of this respiratory syndrome. Most cases have been linked to "street" products or substances added to e-cigarettes -- changes not intended by ecigarette manufacturers. The e-cigarettes used in this study will be obtained directly from JUUL, a manufacturer registered with the FDA, and will not be altered in any way. Overall, the respiratory syndrome associated with e-cigarette use has been reported in less than 1 in 1,000 people who use ecigarettes.

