### **Data Analysis & Statistical Considerations**

 Describe endpoints and power calculations. Provide a detailed description of how study data will be analyzed, including statistical methods used, and how ineligible subjects will be handled and which subjects will be included for analysis. Include planned sample size justification. Provide estimated time to target accrual and accrual rate. Describe interim analysis including plans to stop accrual during monitoring. Phase I studies, include dose escalation schema and criteria for dose escalation with definition of MTD and DLT.

The primary outcome measures will be the amount of combustible cigarette use and e-cigarette use in the last week of the 8-week exposure period. The main index of combustible cigarette use will be expired air CO, a highly sensitive and specific measure of smoke inhalation. As a secondary measure (at the first (V1) and final (V5) sessions), we will assess total urinary 4-(methylnitrosamino)-1-(3-pyridyl)-1-butanol (NNAL), a metabolite of the tobacco-specific carcinogen 4-(methylnitrosamino)-1-(3-pyridyl)-1-butanone (NNK). The half-life of NNAL is 10 days (Goniewicz et al., 2009), yielding a valuable index of sustained reductions in cigarette smoking. The half-life of expired air CO, in contrast, is 4.5 h (Sandberg et al., 2011).

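### Participants unblinded for safety are dropped from the final analyses, an avoidable exclusion after randomisation that can bias the comparison in either direction, probably by a small amount

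*Combined protocol and SAP*

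**What the plan says.** The Emergency Unblinding section lets the study physician or a physician assistant break the blind "in any situation in which unblinding is deemed necessary to ensure or promote the safety of a study participant". Managing a side effect is one of its examples, but the list goes further, to disclosure in order to "uncover potential safety information about the drug, and/or determine whether the adverse event is study related". The section ends by stating that an unblinded participant's "data will be censored and will not be included in final data analyses". There is no condition on this, and data from before and after unblinding are not distinguished.

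In Data Analysis & Statistical Considerations, the template prompt asks for "how ineligible subjects will be handled and which subjects will be included for analysis". The text beneath it describes outcomes, a general linear model, covariates, a one-tailed 5% test and the sample size, but does not answer that question. The unblinding sentence is therefore the only rule in the document on who is analysed.

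Under Design Overview, Group 1 receives nicotine e-cigarettes with a 21 mg patch and Group 2 receives "Zero-nicotine e-cigarettes + 21 mg nicotine skin patches". The arms differ only in inhaled nicotine.

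**The concern.** Randomisation protects the comparison only while group membership in the analysis does not depend on what happened afterwards. Here it does, because a clinician's response to an adverse event can remove a participant. That event may be caused by the assigned product. The Risk/Benefit Assessment notes that "Symptoms associated with nicotine toxicity include lightheadedness, dizziness, nausea, fainting and vomiting", and only Group 1 inhales nicotine on top of the patch. Tolerance of the product plausibly relates to both primary outcomes, e-cigarette use and smoking measured by expired CO.

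The bias could go either way. If Group 1 participants who cannot tolerate the e-cigarette return to smoking and are dropped, Group 1 looks better than it should, and the one-tailed test turns that directly into extra false positives. If heavy e-cigarette users with low CO are dropped, the true effect is understated and power is lost.

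The rule also covers final analyses in general, not efficacy alone. Read literally, a comparison of safety between arms would omit the participants whose events led to unblinding.

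**Working it through.** **Inputs from the plan.** 65 per group (Design Overview); one-tailed alpha 0.05, effect size 0.5, and 50 per group for at least 80% power (Data Analysis & Statistical Considerations). The effect size is read as standardised, so SD = 1.

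**The plan's own figure.** The normal approximation, 1 − Φ(1.645 − 0.5 × √(50/2)) = 1 − Φ(−0.855), gives 80.4% power at 50 per group; the noncentral t gives 79.9%. The stated size reproduces. At 65 per group, power is 88.6% (normal) or 88.3% (t). Since 65 − 50 = 15 per arm could be lost before reaching the planned number, bias matters more here than loss of numbers.

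**Size of the bias.** Let k1 and k2 be the numbers excluded in Groups 1 and 2, and m1 and m2 the amounts by which those excluded exceed their arm's mean, in SD, with higher meaning more smoking. The shift in the group difference is

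k1·m1/(65 − k1) − k2·m2/(65 − k2).

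For three exclusions in Group 1 only, with m1 = 0.926: 3 × 0.926/62 = 0.0448 SD, which is 9% of the planned 0.5 SD. The standard error is √(1/62 + 1/65) = 0.1775. The type I error is then about 1 − Φ(1.645 − 0.0448/0.1775) = 0.082.

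**Simulation.** One normal outcome, 65 per group, one-sided t test at 0.05, 200,000 replicates per scenario (Monte Carlo SE about 0.0005). Participants were removed with probability proportional to exp(s × outcome), with s = 0.5 or 1. Those excluded then average about 0.5 or 0.9 SD worse than their arm. Exclusion counts and s are assumptions. Type I error with no true effect (0.050 with no exclusions):

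| Excluded, Group 1/Group 2 | About 0.5 SD worse | About 0.9 SD worse |
|---|---|---|
| 1/0 | 0.055 | 0.061 |
| 2/1 | 0.055 | 0.062 |
| 3/2 | 0.056 | 0.063 |
| 5/3 | 0.061 | 0.075 |
| 3/0 | 0.066 | 0.085 |
| 3/3 | 0.051 | 0.053 |

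- In the scenarios with unequal counts, the group difference shifts by 0.008 to 0.023 SD (left column) or 0.015 to 0.045 SD (right column), about 1.5% to 9% of 0.5 SD.
- Three Group 1 exclusions who are better than their arm give a type I error of 0.038 (0.5 SD) or 0.030 (0.9 SD). Power at a true 0.5 SD effect falls from 0.88 to 0.85 or 0.82.
- Three Group 1 exclusions unrelated to outcome give 0.050.
- Adjusting for baseline, with an assumed correlation of 0.5, changes the 3/0 row only to 0.064 and 0.079.
- A more extreme case, 5/0 at about 0.9 SD worse, gives about 0.113.

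For scale, 1/0 is 1/130 = 0.8% of participants, 3/0 is 2.3% and 5/3 is 6.2%.

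**Limits.** This is not the planned model, which also adjusts CO for e-cigarette use. E-cigarette use as the other primary outcome was not simulated separately.

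**The case against.** The strongest reply is that few participants will be unblinded and that nothing shows the arms will differ. Patch effects such as disturbed sleep and skin irritation occur in both arms. On nicotine overdose from the e-cigarette, the Risk/Benefit Assessment says "this is extremely unlikely inasmuch as smokers can control the dose according to how they puff and inhale". With balanced exclusions, or exclusions unrelated to outcome, the type I error stays between 0.050 and 0.054. This stands as a limit on size, but it does not justify the rule. No unblinding rate is given, so a small effect is a judgement; the 5/0 case shows what happens if it is wrong.

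A second reply is that a participant who learns the allocation may behave differently. The section, however, describes telling the clinician, not the participant. The coordinator and program leader already know every allocation without any data being dropped for that reason. CO is objective and can still be measured. Where a participant does learn the allocation, a sensitivity analysis is enough.

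A third reply is that rewording may not recover the outcome. In-person visits carry the rule that "if participants miss two consecutive visits they will be withdrawn from the study", and Remote Study Participation has the same rule for milestones. Remote participants also receive the second CO monitor only after completing e-visits 1 to 4. This is correct. In the 3/0 case at about 0.9 SD, if one or two of the three had no V5 CO in any event, a complete-case type I error of about 0.060 or 0.073 would remain after the change. Missing Data Forms are provided for, but no statistical method for missing outcomes is stated.

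**Conclusion.** The concern holds. The plan contains an unconditional exclusion after randomisation, its trigger may depend on treatment, and nothing overrides it. Confidence is high that the rule exists and is avoidable, and low on the size of its effect. With one to three outcome-related exclusions confined to Group 1, the shift is about 1.5% to 9% of the planned effect. The type I error lies between 0.055 and 0.085 if those excluded are worse than their arm; for 3/0 it is between 0.030 and 0.038 if they are better. These figures illustrate the mechanism under assumed counts and outcome differences; they are not bounds. Bias requires exclusions that differ by arm in number or type and that are related to outcome. The effect is probably small, but the exclusion gains nothing and should be changed.

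**What to change.** Replace the last sentence of the Emergency Unblinding section with text such as:

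> Participants whose allocation is disclosed under this section remain in the primary analysis in the arm to which they were randomised, using all outcome data collected before and after disclosure. Scheduled outcome collection, including the V5 CO reading, continues where the participant agrees. An analysis excluding these participants is reported as a sensitivity analysis only, with the number and reasons for unblinding by arm.

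Include these participants in any safety summary. No change to the clinical unblinding process is proposed.

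The cost is a short text change and V5 collection for the few people affected. The two-consecutive-miss withdrawal rules (Sessions; Remote Study Participation) and the condition for sending the second CO monitor must be reconciled with this text, so that they do not by themselves prevent V5 collection. Where no V5 CO exists, the new wording restores no outcome. A small downside is that some later behaviour may reflect knowledge of allocation, which the sensitivity analysis addresses.

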### Privacy, Data Storage & Confidentiality

• Complete the Privacy and Confidentiality section of the iRIS submission form.

### **Describe Role of External Personnel:**

External key personnel will assist in data collection, data entry, data analysis, and recruitment under the supervision of our staff. They will also shadow all aspects of the research process, including consent, but will not be conducting consent independently. They will not be accessing Maestro or OnCore but will have access to our paper and electronic PHI in REDCap (name, address, phone, DOB, medical history, SSN for payment). Onsite training on research practices, confidentiality/privacy, and HIPAA will be conducted during their first week.

Does the subject population contain >50% malignant hematology or oncology patients, or their caregivers?
O Yes 💿 No
Are you using a drug, biologic, food, or dietary supplement in this study?
⊙ Yes O No
Are you using a medical device, an algorithm (whether computer based or not), an in vitro diagnostic test, or using samples to look for biomarkers in this study?
⊙ Yes O No
Does this study involve a Humanitarian Use Device (HUD)?
O Yes 💿 No
Does this study employ magnetic resonance, including imaging (MRI), spectroscopy (MRS), angiography (MRA) or elastography (MRE) beyond the standard of care?
O Yes 💿 No
Does this study specify or require the performance of diagnostic procedures using ionizing radiation (x-rays, DEXA, CT scans, nuclear medicine scans, etc.) that are beyond the standard of care?
O Yes 💿 No
Does this study specify or require the performance of therapeutic procedures using ionizing radiation (accelerator, brachytherapy or systemic radionuclide therapy) that are beyond the standard of care?
O Yes 💿 No
Will the participant be subjected to increased or decreased ambient pressure?
O Yes 💿 No
Do you plan to recruit subjects from Duke Regional Hospital (DRH)?
O Yes 💿 No
Do you plan to recruit subjects from Duke Raleigh Hospital (DRAH)?
O Yes 💿 No
Does this study utilize the Duke Early Phase Clinical Research Unit (DEPCRU)?
O Yes 💿 No
Are you using the Duke logo in any advertisements?

Is this study retrospective, prospective, or both?	

 
"Retrospective" means that data or samples already in existence (collected prior to the study submission) will be used.
 
"Prospective" means there will be data or samples collected in this study for research purposes.
 
Retrospective
 
Prospective
 
Retrospective and Prospective: Is this a review soley of information collected for non-
 
	
O Yes O No	
Does this protocol include any research using botulinum toxin, including the FDA-approved clinical product (Botox)?	
O Yes 💿 No	
Does this protocol involve the administration of any of the following materials to humans?	

 
Any viral vector or plasmid
 
Any cells that have been modified by a viral vector
 
Any other genetically-modified cells
 
Any genetically-modified virus, bacterium, or other agent
 
Any other recombinant or synthetic nucleic acid
 
Yes  
 
No
 
 
 
	
Subject Population Groups and Enrollment	
Population Groups (Select targeted population groups only):	
ropulation croups (ociect largeteu population groups only).	

 
Note:
 
If Minors are included, the study will be routed to the Department of Pediatrics for Pediatric Risk Assessment.
 
Students and Employees over whom Key Personnel have a supervisory role may not be enrolled in this study
 
	

Blanket Protocol
Students and Employees over whom Key Personnel have a supervisory role may not be enrolled in this study.
Please select any population groups excluded from participation in this study:
✓ Pregnant women
Will you administer a pregnancy test to eligible female subjects prior to the start of study activities?
• Yes O No
Maximum number of subjects to be consented at Duke:
Enter a single number. If you anticipate consenting a range of subjects, enter the upper limit of the range. The number should represent the maximum number of subjects for the life of the study. 1600
Maximum number of subjects to be consented at all sites:
Enter a single number. If you anticipate consenting a range of subjects, enter the upper limit of the range. The number should represent the maximum number of subjects for the life of the study. 1600
Subject Procedures and Costs
Biobank - Does this study involve the collection, use, tracking, banking (storage) or distribution of human biological specimens?
Human biological specimens include blood or its components, healthy or diseased tissue, bodily fluids, DNA /RNA or human stem cells.
⊙ Yes O No
Procedures
Check all the apply:

 
Genetic Testing
 
Gene Transfer
 

- 🔲 DNA Banking
- Testing for Reportable Infectious Diseases
- Human Cell Banking
- \*Use of Human Embryonic Stem Cells
- \*Use of Human-induced Pluripotent Stem Cells
- □ \*Use of Other Cells Derived from Human Embryos
- \*Use of Human/Animal Chimeric Cells
- □ \*Specialized Cell Populations for Cell Therapy
- 🔲 Use of Human Tissue
- ☑ Use of Bodily Fluids
- Use of Blood (or its components)
- Not Applicable

Will blood be drawn in this study for research purposes?

O Yes 💿 No				
Will the Operating Room be used in this study?				
Include only research time, not clinical care time. O Yes O No				
Will there be extra costs to subjects or insurance as a result of the research (e.g. tests, hospitalization)?				
O Yes 💿 No				
Will there be Subject Compensation?				
⊙ Yes ○ No				
Compensation for Travel / Lost Income (in USD):				
335				
Other Subject Compensation: None				
Subject Recruitment Materials				
For each document to be reviewed, use the table below to provide the following information:				

Attach a copy of each advertisement that you will be using with this study in the Initial Submission Packet. If any Ad will have multiple wording variations, attach a copy of each version of the Ad.

All materials that will be used to advertise the study in order to recruit subjects must be approved by the IRB.

Types of subject recruitment materials include, but are not limited to, the following:

